PK	pharmacokinetic
PLATFORM	Science 37 Platform
PPS	Per Protocol Set
PS	Patient Safety
PT	preferred term
RLS	Restless Legs Syndrome
RLS-QoL	Restless Legs Syndrome-Quality of Life
RLS-6	Restless Legs-6 Rating Scales
RS	Randomized Set
SAE	serious adverse event
SAP	Statistical Analysis Plan
SBP	systolic blood pressure
SD	standard deviation
SOC	system organ class
SOP	Standard Operating Procedure
SS	Safety Set
TEAE	treatment-emergent adverse event
ULN	upper limit of normal
WMP	Where's My Patch

1 SUMMARY

This is a Phase 3, remote, double-blind, randomized, adaptive, placebo-controlled study of fixed dose administration of rotigotine transdermal system in adolescent subjects, 13 to 17 years of age, with idiopathic Restless Legs Syndrome (RLS). Subjects will be randomized to 1 of 3 treatment groups: placebo, 2mg/24h rotigotine, or 3mg/24h rotigotine.

The total study duration per subject will be up to 24 weeks including a 4-week Screening Period, a 3-week Titration Period, 12-week Maintenance Period, a Taper Period of 4 days (with de-escalation by 1 dose step every 2 days), and a 30-day Safety Follow-Up Period (for subjects not participating in the open-label, long-term follow-up study). The end of the study is defined as the last visit of the last subject in the study.

A total of 138 subjects are planned to be randomized during the study. A single remote site in the USA is planned to be included in the study. This model integrates telemedicine technology into the clinical research process and supports management of research activities, including data collection.

The primary objective of this study is to demonstrate the efficacy of rotigotine against placebo in adolescent subjects with idiopathic RLS over a 12-week Maintenance Period. The secondary objectives are to investigate the efficacy, safety, and tolerability of rotigotine in adolescent subjects.

The co-primary efficacy variables are change from Baseline to the end of the Maintenance Period in International Restless Legs Rating Scale (IRLS) sum score and change from Baseline to the end of the Maintenance Period in Clinical Global Impressions (CGI) Item 1 score.

Other efficacy variables are change from Baseline by visit in IRLS sum score and Restless Legs-6 Rating Scales (RLS-6).

Safety variables are adverse events (AEs), withdrawals due to AEs, physical and neurological examination findings, changes from Baseline in 12-lead electrocardiograms (ECGs), vital signs, laboratory data, hormone status, body weight, height, body mass index (BMI), and Modified Minnesota Impulsive Disorder Interview (mMIDI).

2 INTRODUCTION

Restless Legs Syndrome, also known as Willis-Ekbom disease, is a common pediatric neurologic condition affecting 2% to 4% of school-aged children and adolescents, with about 25% to 50% of pediatric cases having moderate-to-severe symptoms. Restless Legs Syndrome has a significant impact on sleep, mood, cognition, and function, particularly sleep disturbance. Impairment is often manifested in behavioral and educational domains (Pichiatti et al, 2013). Genetic factors, dopamine dysfunction, and low-iron stores may play a role in the pathophysiology of RLS (Simakajornboon et al, 2009). Current evidence supports relative iron deficiency and renal failure as potential aggravating factors for pediatric RLS. Periodic limb movements in sleep and a family history of RLS among first-degree relatives are supportive of pediatric RLS (Pichiatti et al, 2013).

The pediatric RLS diagnostic criteria were published in 2003 based on the consensus at a National Institutes of Health workshop (2002) sponsored in part by the International RLS Study Group. These diagnostic criteria were updated in 2013 by the International RLS Study Group

(Picchietti et al, 2013). Ruling out RLS mimics was integrated as an essential element for RLS diagnosis.

Dopaminergic agents are the first-choice treatment for RLS in adults; however, to date, no treatment for RLS has been approved for children. Small published reports suggest that dopamine agonists are effective in the management of RLS in children (Simakajornboon et al, 2009; Cortese et al, 2009; Muhle et al, 2008; Mohri et al, 2008; Konofal et al, 2005; Guilleminault et al, 2003).

The investigational medicinal product (IMP) is a transdermal formulation of the dopamine agonist rotigotine. The patch is applied to the skin and provides constant plasma concentrations. It was first approved by the European regulatory authorities for use in patients with Parkinson's disease in March 2006, and by the US Food and Drug Administration (FDA) in May 2007. Rotigotine transdermal system was approved by the FDA as a treatment for adult patients with RLS in April 2012.

The tolerability of rotigotine transdermal system appears to be within the range of what is known and expected from other dopamine agonists, except for application site reactions, which appear to be mild to moderate in the majority of cases (Perez-Lloret et al, 2013).

UCB has completed a Phase 2 pharmacokinetic (PK)/pharmacodynamic (PD) study in adolescent subjects 13 to 17 years of age, which showed a PK profile similar to that in adult subjects. Although the study was open-label and the sample size was small, the efficacy of rotigotine transdermal system in adolescent subjects also appeared similar to efficacy in adults. Improvements were observed in most efficacy parameters, including the IRLS, CGI Items 1 through 3, and RLS-6, indicating improvements in RLS symptoms and sleep. The purpose of this study is to further investigate the efficacy, safety, and tolerability of rotigotine in adolescent subjects 13 to 17 years of age.

A remote study model will be used to conduct this study. This model integrates telemedicine technology into the clinical research process and supports management of research activities, including data collection. As part of this model, study visits are completed using the unique technology platform called Science 37 Platform, or PLATFORM, which is the backbone of the studies conducted via this model. PLATFORM is the software interface that connects subjects/legal representatives to their investigators/study teams through a study-issued smartphone. This technology will be used in combination with visits from mobile study personnel to subjects'/legal representatives' homes.

3 STUDY OBJECTIVES

The primary objective of this study is to demonstrate the efficacy of rotigotine against placebo in adolescent subjects with idiopathic RLS over a 12-week Maintenance Period. The secondary objectives are to investigate the safety and tolerability of rotigotine in adolescent subjects with idiopathic RLS.

4 STUDY VARIABLES

4.1 Efficacy variables

4.1.1 Primary efficacy variable

The co-primary efficacy variables are change from Baseline to the end of the Maintenance Period in IRLS sum score and change from Baseline in CGI Item 1 to the end of the Maintenance Period.

4.1.2 Secondary efficacy variables

Secondary efficacy variables include:

- Change from Baseline in RLS-6 Rating Scales to the end of the Maintenance Period

4.1.3 Other efficacy variables

- Change from Baseline in CGI Item 1 by visit*
- Change from Baseline in RLS-6 Rating Scales by visit*
- Change from Baseline in IRLS sum score by visit*
- IRLS Responder: A responder is defined as a subject with a decrease of $\geq 50\%$ in IRLS sum score from Baseline
- IRLS Remitter: Two definitions for IRLS remitter will be used in the study; a remitter is defined as a subject with an IRLS sum score ≤ 10 points or a subject who is symptom free (ie, IRLS sum score of 0 points)
- CGI Item 1 Responder: A responder is defined as a subject with a decrease of $\geq 50\%$ in CGI Item 1

*For the IRLS, CGI, and RLS-6, the End of Maintenance (EoM) Visit is already covered under primary and secondary variables.

4.2 Safety variables

4.2.1 Primary safety variables

- Occurrence of TEAEs
- TEAEs leading to withdrawals

4.2.2 Other safety variables

- Changes from Baseline (Visit 1) in 12-lead ECGs
- Changes from Baseline (Visit 1) in vital signs (including assessment of orthostasis)
- Changes from Baseline (Visit 1) in laboratory data (hematology, blood chemistry, and urinalysis)
- Changes from Baseline (Visit 1) in hormone status
- Changes from Baseline (Visit 1) in body weight, height, and BMI
- Changes in mMIDI

- Changes in menstrual function for all female subjects

4.3 Other variables

Other variables include:

- Plasma concentrations of unconjugated rotigotine
- Subject Quality of Life Questionnaire

5 STUDY DESIGN

5.1 Study description

This is a Phase 3, remote, double-blind, randomized, adaptive placebo-controlled study of fixed dose administration of the rotigotine transdermal system. The study will be conducted in adolescent subjects, 13 to 17 years of age, with idiopathic RLS. Subjects will be randomized to 1 of 3 treatment groups: placebo, 2mg/24h rotigotine, or 3mg/24h rotigotine.

The study will be conducted using the remote study model, which uses telemedicine technology (ie, PLATFORM, see [Section 2](#) for an overview) for interactions between the investigator/study staff and study subjects/legal representatives. Mobile study personnel will visit subjects'/legal representatives' homes to complete certain study procedures (eg, neurological exams, physical exams, ECGs, lab collections, and vital signs).

The study will also utilize a reminder app to help maximize retention of study subjects and limit dropouts. The app, located on the study smartphone, called Where's My Patch (WMP) will help encourage subject adherence to study medication administration by reminding them to place patches at their prespecified time each day. It also provides a body map to record daily patch locations as a visual reminder of where patches have already been placed over the past 14 days and to facilitate patch site rotation. Patch location data will only be retained locally on the smartphone and then automatically deleted after 14 days. Subject use of the MWP app will be encouraged, but not required.

The study will begin with a Screening Period of at least 7 days (maximum of 28 days) prior to Visit 2/Baseline to ensure homogeneous baseline conditions can be established for all subjects. Subjects with prior intake of any dopamine agonists or taking L-dopa must discontinue the therapy at least 7 days prior to Visit 2/Baseline. Discontinuation of therapy must be driven by the subject's medical need and not undertaken for the purpose of making a potential subject eligible for the study.

The Screening Period will be followed by the Titration Period. Subjects will receive their first dose of study medication at Visit 3/Day 1. Subjects will be initiated either on placebo or 1mg/24h rotigotine. The dose of rotigotine taken by subjects randomized to rotigotine will then be up-titrated on a weekly basis by 1mg/24h at a time to 2mg/24h or 3mg/24h, depending on the subject's assigned dose level.

Subjects will be administered study medication according to the dose titration schedule in [Section 7.2.1](#).

Subjects will be allowed to back-titrate 1 dose level during the Titration Period. Subjects are to complete the Titration Period at the back-titrated dose level and remain at this dose level for the duration of the Maintenance Period. If AEs occur during the Titration Period that are thought to

be the result of excessive dopaminergic stimulation (eg, intolerable nausea/vomiting), subjects should be back-titrated to their previous dose level and commence the Maintenance Period immediately. Subjects who do not tolerate the assigned dose in the first week (placebo or 1mg/24h) will be withdrawn from the study. If subjects withdraw due to lack of efficacy, they are eligible to roll over to the open-label study, RL0007, after the 3 weeks of the Titration Period are completed.

The Titration Period will be followed by a 12-week Maintenance Period. Subjects will remain at the assigned (or back-titrated) dose level throughout the Maintenance Period. At the end of the Maintenance Period, subjects will enter a Taper Period lasting up to a maximum of 4 days (de-escalation of study medication), followed by a 30-day Safety Follow-Up Period.

Visits will be scheduled every week during the Titration Period. During the Maintenance Period, visits will be scheduled every 4 weeks. There is a 4-day interval until the end of the Taper Period, followed by a 30-day interval (± 5 days) until the Safety Follow-Up Visit. Details are provided in the schedule of study assessments in [Section 5.2](#).

Plasma concentration of unconjugated rotigotine will be summarized by dose levels and visit. Plasma samples will be collected at Visit 6 and Visit 9.

An interim analysis for futility (for the primary outcome measures only), with the possibility of stopping the study early, stopping a dose arm, or continuing the study as planned, will be performed with approximately 33% of the planned number of evaluable subjects; recruitment will not be stopped for the interim analysis. The futility criteria are defined in [Section 13.7](#).

An overview of the study activities is given in [Table 5-1](#) and [Figure 5-1](#).

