	Day -28 to Day -1	Day 0	Day 1	Day 8	Day 15	Day 22	Day 50	Day 78	Day 106	Day 110		
Assessment												

BL=Baseline; BMI=body mass index; CGI=Clinical Global Impressions; C-SSRS=Columbia-Suicide Severity Rating Scale; ECG=electrocardiogram; eCRF=electronic Case Report form; EOT=End of Titration; hCG=human chorionic gonadotropin; IRLS=International Restless Legs Scale; IRT=interactive response technology; mMIDI=Modified Minnesota Impulsive Disorder Interview; PK=pharmacokinetic; Rand=randomization; RLS=Restless Legs Syndrome; SOM=Start of Maintenance; V=Visit; WD=withdrawal

Note: The date of informed consent may be prior to screening assessments and study procedures.

Note: Rescreening is allowed with the permission of the Study Physician or representative.

Note: For Visit 2, there is a visit window of +3 days to allow for direct-to-subject shipment of study medication. Visit 3/Day 1 is the first day of study medication exposure. All subsequent visits are calculated based on Visit 3/Day 1.

Note: Visit 6 is the end of the Titration Period and start of the Maintenance Period. Visit 9 is the end of the Maintenance Period and start of the Taper Period.

Note: All visits are via telemedicine calls, with the exception of Visit 1, Visit 6, Visit 9, and SFU. Unscheduled visits are at the discretion of the investigator and may be telemedicine calls.

^a The visit window for Titration Visits is ±1 day per visit relative to Visit 3 (day of first dose). The visit window for visits during the Maintenance Period, including the End of Maintenance Visit, is ±2 days per visit. The Taper Period, which will last up to a maximum of 4 days, will start on the day after the End of Maintenance Visit. The visit window for Safety Follow-Up Period is 30 days±5 days relative to the end of the Taper Period. Following dose de-escalation, subjects may be eligible to participate in the open-label, long-term follow-up study (RL0007) at any time prior to the Safety Follow-Up Visit (see Section 5). The Safety Follow-Up Visit is for subjects not entering RL0007.

^b Assessments to be performed are at the investigator's discretion.

^c C-SSRS is required if the Un-scheduled Visit is conducted due to safety or efficacy reasons.

^d Pregnancy test and menstrual function for all female subjects; serum pregnancy test at Screening and urine pregnancy test at all other visits. A positive urine pregnancy test must be confirmed by a serum pregnancy test.

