5.3 Schematic diagram

Subjects will be randomized to 1 of 3 treatment groups:

Figure 5–1: Schematic diagram

* Two patch sizes will be used: 5cm² and 10cm². Placebo patches will be identical in size and appearance to active patches.

- Subjects will remain at the assigned dose level throughout the 12-week Maintenance Period.
- Subjects will be allowed to back-titrate 1 dose level during the Titration Period. See [Section 5.1](#).
- Subjects will complete the Titration Period at the back-titrated dose level and remain at this dose level for the duration of the Maintenance Period.

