7.2.1.1 Maintenance Period

The Titration Period will be followed by a 12-week Maintenance Period. Subjects will maintain doses achieved at Visit 6 (end of the Titration Period) throughout the Maintenance Period. During the Maintenance Period, visits will be scheduled every 4 weeks for 3 visits.

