8.2.1 Visit 2 (Baseline)

The following assessments will be performed via telemedicine call. The visit window for Visit 2/Baseline is +3 days.

Information and procedures listed below will be collected/completed by the investigator and/or study staff, as appropriate, via a telephone or telemedicine call with the subject/legal representative. Eligibility may only be confirmed once all the procedures noted for screening are completed, and results are obtained and reviewed.

- Eligibility criteria
- Withdrawal criteria

- Menstrual function for all female subjects

Assessments listed below will be completed by either the subject or investigator/trained study staff, as required. Assessments that require interviews will be completed via a telephone or telemedicine call.

- C-SSRS (Since Last Visit version)
- IRLS (at Baseline, subjects must score ≥ 15 on the IRLS Rating Scale [indicating moderate-to-severe RLS])
- CGI (at Baseline, Subjects must score ≥ 4 points on the CGI Item 1 assessment [indicating at least moderately ill])
- RLS-6
- Subject Quality of Life Questionnaire

Additional assessments and procedures are listed below.

- Recording of medication and procedures. Medications and procedures will be reviewed with the subject/legal representative by the investigator/designated study staff via a telephone or telemedicine call and noted as part of the subject's study record.
- AE assessment. All AEs will be assessed and reviewed throughout the study.
- Contact IRT. Once eligibility is confirmed (see above), the IRT will be contacted to obtain the assigned randomization number and study medication kit numbers for the Titration Period.
- Once randomization is completed, study medication for the Titration Period will be assigned and shipped to the subject/legal representatives home for receipt on Day 1. See [Section 7.5](#) for a description of the direct-to-subject shipment process for the remote study model.

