8.2.2 Visit 3 (Day 1)

Visit 3/Day 1 is the first day of study medication exposure. All subsequent visits are calculated based on Visit 3/Day 1.

The following assessments will be performed.

- Withdrawal criteria
- C-SSRS (Since Last Visit version)

The subject will apply their first patch during the visit under the supervision of the investigator (or designee) via a telemedicine call.

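### Does telling back-titrated subjects to start Maintenance at once upset the Day 1 visit calendar or the analysis?

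*Protocol*

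**What the plan says.** Protocol Section 5.1, repeated in Section 7.2.1, gives two instructions in consecutive sentences. The general one is "Subjects are to complete the Titration Period at the back-titrated dose level", with that dose then held through Maintenance. The second covers adverse events attributed to excessive dopaminergic stimulation: "subjects should be back-titrated to their previous dose level and commence the Maintenance Period immediately".

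The rest of the protocol describes one calendar:
- Section 8.2.2 and the notes to Table 5-1: "All subsequent visits are calculated based on Visit 3/Day 1".
- Notes to Table 5-1: "Visit 6 is the end of the Titration Period and start of the Maintenance Period".
- Section 5.3 carries only the general instruction: "Subjects will complete the Titration Period at the back-titrated dose level and remain at this dose level".
- Section 7.2.1.1: "Subjects will maintain doses achieved at Visit 6 (end of the Titration Period) throughout the Maintenance Period".
- Section 8.2.1 assigns "study medication kit numbers for the Titration Period" at Visit 2. Section 8.3.1 assigns the Maintenance kits at Visit 6.
- Table 7-3 places the taper on Days 107 to 110 in every dose row.

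SAP Section 2.3 summarises the back-titration rule and leaves out the second sentence. SAP Section 3.2.2 starts Maintenance at Visit 6. SAP Section 10.1 takes the final dose at Visit 6 and names the back-titrated case.

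**The concern.** Neither sentence is marked as an exception to the other, and the only reason given for a step down is the one in the second sentence. Read as a calendar instruction, an early start raises questions that the protocol does not answer: whether the 12 weeks and the four-weekly visits run from the step down or from Day 22, and whether Visit 9 moves with them.

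If it moved, the co-primary assessments (IRLS sum score and CGI Item 1 at the end of Maintenance) would come after a shorter total exposure in some subjects. Back-titration for dopaminergic effects is also likely to be more common on active drug than on placebo, so the shift could differ by arm. That would be a real problem for the efficacy comparison, so the text needed checking.

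**Working it through.** **The plan's own calendar.** Inputs: first patch on Day 1, 3 weeks of Titration, 12 weeks of Maintenance, visits every 4 weeks (Protocol Section 5.1, Table 5-1).
- Visit 6: 1 + 21 = Day 22
- Visits 7, 8 and 9: 22 + 28 = Day 50; 22 + 56 = Day 78; 22 + 84 = Day 106
- Total length: 28 + 21 + 84 + 4 + 30 = 167 days, and 167 / 7 = 23.9 weeks, against the stated maximum of 24

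The stated calendar is reproduced exactly with Maintenance starting on Day 22.

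**Earliest step down.** Table 7-2 begins the higher dose on Day 8. Subjects who do not tolerate the first-week dose are withdrawn (Section 5.1). The step down therefore falls on day d, with d from 8 to 21.

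**Size of the labelling gap, with visits on time.** Days called Maintenance by the second sentence and Titration elsewhere = 22 − d. Length of Maintenance by the second sentence = 106 − d.

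| Step down (d) | 22 − d | 106 − d | Planned length |
|---|---|---|---|
| Day 8 | 14 | 98 | 84 |
| Day 15 | 7 | 91 | 84 |
| Day 21 | 1 | 85 | 84 |

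SAP Section 3.2.3 allows Visit 6 a window of ±2 days. With Visit 6 on Day 24 the gap is at most 24 − 8 = 16 days.

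**Does anything besides the label move?**
- *Dose.* Both sentences have the subject step down one level and stay there. Section 7.2.1.1 carries the Visit 6 dose forward, which is that same dose.
- *Visits.* The Day 1 anchor has no exception for back-titrated subjects.
- *Taper.* Table 7-3 has a row for 1mg/24h on Days 107 to 110. The randomised targets are 2 and 3mg/24h, so a subject is at 1mg/24h at the end of Maintenance only through back-titration. The protocol thus places back-titrated subjects on the ordinary calendar.
- *Efficacy analysis.* The model in Protocol Section 13.3.1 has visit as a factor, not study period. SAP Section 8.1.2 summarises by visit and by randomised group. The Titration/Maintenance boundary enters neither.
- *Adverse events.* SAP Section 10.2 uses the whole Treatment Period, so a boundary inside it has no effect.
- *Displays that do use the boundary.* Disposition by period (SAP Section 5.1) and the exposure summaries (SAP Section 10.1) depend on it. For a subject who steps down and leaves before Visit 6, the label would matter. SAP Section 3.2.2 settles that case: the subject withdrew during Titration.

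**A phrase that does not bear on this.** The wording "after the 3 weeks of the Titration Period are completed" in Section 5.1 concerns entry to the open-label study after withdrawal for lack of efficacy. It sets no rule for subjects back-titrated for adverse events.

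**The case for a change.** The strongest case for acting is that Maintenance is a defined period with its own length and visit spacing, so telling a site to commence it is more than a label. A site could have counted 84 days from the step down; from Day 8 that gives 8 + 84 = Day 92, which is 14 days before Day 106. SAP Section 3.2.3 makes no visit correction, so the result would still be tabulated as Visit 9. SAP Section 3.9, which lists changes from the protocol, does not mention that the SAP follows only one of the two sentences.

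The textual part of this stands: the sentences do not agree, and treating the second as an exception still leaves its timing unstated. The consequence does not follow. Moving Visit 9 would require a site to set aside the Day 1 anchor, and the Maintenance kits are assigned only at Visit 6. It would be a departure from the protocol, not a result of following it. It would also be visible: SAP Section 3.2.1.1 puts the relative day of each visit in the listings, SAP Section 3.2.3 gives Visit 9 a ±2-day window for identifying important deviations, and SAP Section 5.2 summarises and lists those deviations.

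**Conclusion.** The inconsistency is real but clerical. It affects the name given to 14 days down to 1 day per back-titrated subject with on-time visits, and at most 16 days with a late Visit 6. It leaves the dose, the visit days, the taper days and every efficacy summary unchanged. Where the period boundary does enter a table, the SAP already defines it by Visit 6.

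This rests on sites having kept the Day 1 anchor that the protocol states, and on back-titration not occurring before Day 8. The documents do not say how many subjects were back-titrated, so no frequency can be given. The study was terminated early and efficacy is now summarised descriptively (SAP Sections 1 and 8.1.2), which leaves still less that could depend on the wording.

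The two sentences must be reconciled if the text is reissued, and which one governs is for the sponsor to decide. That is an editorial matter with no gain for the results, so no change to the plan is called for.
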